B4. Chinese Americans, socio-cultural barriers and lifestyle-related stomach cancer risk factors. *Health care access.* For Chinese American communities, the risk of stomach cancer is compounded by difficulties in accessing healthcare services, and attendant linguistic, cultural, economic and social barriers, which contribute to delayed cancer screenings,²¹⁻²⁴ poor medication adherence, and poor disease self-management skills.²⁵⁻²⁸ *Acculturation* (which includes indicators such as nativity, years in the US, English language proficiency) is a significant factor that influences health access and behaviors for Chinese American immigrant communities, including impacting screening and disease prevention.^{25,26}

B5. Evidence-base for test-and-treat in high-risk Chinese populations.

The American College of Gastroenterology's 2017 clinical guidelines for treating *H. pylori* infection recommends clarithromycin triple therapy consisting of a proton pump inhibitor (PPI), clarithromycin, and amoxicillin or metronidazole for 14 days where *H. pylori* clarithromycin resistance is known to be <15%.²⁹ This is an oral regimen of 6-8 pills taken daily at different dosing intervals for 14 days. Test for treatment success of eradication therapy should occur at least 4 weeks after completion of antibiotics and with patients off PPI for 1-2 weeks, using urea breath test, fecal antigen test, endoscopic testing or other clinically approved *H. pylori* infection diagnostic test.

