CHW Components. We will refine the CHW protocol and curriculum. We will conduct a scan of CHW and/or care coordination efforts at the sites to determine possible leverage points for the placement of CHW initiatives or opportunities to support train-the-trainer models. The advisory group will also review any existing materials, adapt them culturally and linguistically for the target population, and integrate with the existing pilot CHW educational curriculum. The Ecological Validity Model⁷⁸ complemented by a social marketing approach⁷⁹ will be applied, to assess and adapt the materials. Small media materials will be produced by the advisory group using a participatory process, adapted from our previous studies,⁸⁰⁻⁸² and may include bilingual palm cards and pamphlets on *H. pylori* eradication therapy, side effects and stomach cancer prevention.

To enhance scientific rigor, measure selection was based on: 1) brevity; 2) presence of domains with face validity for Asian American or low-literacy communities; and 3) valid psychometric properties. The **primary outcome** measure is the most rigorous outcome measure related to *H. pylori* eradication: confirmation of *H. pylori* eradication by fecal antigen test or other clinically approved *H. pylori* infection diagnostic test conducted 4 weeks–3 months post-treatment (to be extracted from EHR). **Secondary outcomes** include: self-efficacy, health literacy, medication adherence and other factors. Medication adherence measured using simplified medication adherence questionnaire (SMAQ) and medication adherence report scale (MARS-5). Self-efficacy will be measured by the Ottawa Decision Self-Efficacy Scale. Health literacy will be assessed using the short form of the European Health Literacy Survey Questionnaire (HLS-EU-Q12). Health-related quality of life will be measured by the Patient-Reported Outcome Measurement Information System Global Health Scale (PROMIS).⁸⁶

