CHW Intervention Components. The intervention arm protocol consists of 4 educational sessions: session 1 will focus on medication adherence, treatment side effects, and the link between *H. pylori* and stomach cancer; and sessions 2 through 4 will focus on reinforcing session 1 themes, stomach cancer risk reduction, and links to community-based resources. The sessions employ adult learning techniques and group-based learning activities. All session materials are culturally and linguistically adapted. The in-person sessions will be held at the clinics, community spaces identified by partner agencies or by telephone. These sessions will be accompanied by phone call, text or voicemail medication and follow-up reminders in the preferred language (frequency depending on participant preference). The intervention materials will model scripts and messages informed by Social Cognitive Theory and will include reviewing and reinforcing individualized challenges, strategies and action plans for medication adherence and stomach cancer prevention.

A2. Data Collection

The recruitment and data collection protocol will be finalized with substantial feedback from the advisory group. All study staff involved in recruitment and data collection will receive a standardized training orientation on administering surveys and will be certified in human subjects research via the Collaborative Institutional Training Initiative (CITI Program).

EHR data will be used for recruitment and for the determination of primary outcomes. [name] will work with MCIT to identify potential participants from EPIC databases. During the recruitment period, registry lists will be generated weekly from EHR for physicians who have approved participation of their patients. Patients will be contacted either by phone (up to 3 calls) or in person by CHW. All preliminary EHR data will be deleted or shredded after one week of retrieval. EHR data to be shared with the study team include: demographics (gender, age, race/ethnicity (if available), language (if available), diagnosis of *H. pylori* through ICD codes, dates of clinic visits, name, and telephone number. Scheduled office visits will be tracked via quarterly EHR data pulls. EHR data will also be used to follow-up with the

outcome of treatment regimens and to determine *H.pylori* eradication via fecal stool antigen tests based on treatment follow-up procedures of physicians.

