Contact information will be collected from participants, including cell phone and home phone numbers, home and work address, email address, and Facebook/social networking account information. We will also assess whether participants are willing to receive text reminders on their cell phone. Additionally, a reminder letter and a small gift (tote bag, etc) will be sent to every participant who is willing to receive mail 4 months after enrollment. These strategies have been shown to be effective in retaining participants in community-based research.

Data will be collected by study staff via surveys at baseline, 2, and 6 months. Scheduled office visits will be tracked via quarterly data pulls from the EHR system. If no visit is scheduled during the follow-up period, project CHWs will conduct follow-up calls to schedule participants for data collection events in the community, at the clinic, or at their home, with permission. Participants will be compensated \$25 for each assessments and will receive reminder calls and/or texts 2 weeks prior to data collection events to ensure attendance.

Substudy Biosample Collection. Substudy participants will have the option of mail or in-person pick-up for receiving study materials, which include the kits to collect oral wash and/or fecal samples and return stamped envelope. Once the substudy materials are received, study staff will set up an appointment to call or meet with substudy subjects remotely via WebEx and answer any questions about sample collection and return.

Substudy subjects will have the option to provide oral wash sample only, fecal sample only, or both. Study staff who have obtained the verbal consent will document the consent on the Enrolled Participants Log. The Enrolled Participants Log is the only record linking a participant's name, subject ID and substudy ID (if applicable).

Fecal biosample collection: Substudy participants will provide fecal samples (about 8 grams which is about 2 teaspoons) in a OMNIgeneGUT fecal sample tube (*DNAgenotek, Ontario, Canada*).

Directions for performing the test:

- 1) Remove the fecal sample tube with preservation liquid inside from packaging.
- 2) Flush the toilet, allow it to refill. The stool cannot touch the toilet bowl or water. Use one of the following collection options:
 - a. Place saran wrap or provided stool collection paper over the toilet bowl to collect a sample of stool.

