 - b. Just before finishing a bowel movement, use a piece of toilet paper to collect a small sample of stool.
- 3) Use spoon attached to cap to collect 2 marble sized samples.
- 4) Carefully screw the cap closed with sample on spoon. Shake well.
- 5) Once the collection is complete, place the tube in the preaddressed package and seal carefully. Return to the study center by mail within one day of collection.

Oral wash biosample collection: Study participants will be asked to swish vigorously with one aliquot of 10 ml Scope Original mouthwash sample (*Proctor & Gamble, Cincinnati, OH*) for 30 seconds.

Participants will be directed to expectorate the mouthwash into a clean specimen tube, and return to the study center by mail within one day of collection.

B. Data Analysis and Data Monitoring

B1. EHR-CHW Intervention Analysis.

We will conduct analyses to determine the comparability of the participants in the 2-arms using standard techniques, including Student's t-tests for normally distributed variables (after necessary transformations) and chi-squared tests for dichotomous variables. If the randomized groups differ in baseline characteristics, we will adjust for those variables in subsequent analyses of program effects. Descriptive statistics will be calculated to characterize study participants and to evaluate the distribution of key clinical, sociodemographic, and outcome variables. Summary data on medical history, years in the US, access to and utilization of primary health care services, and social characteristics (e.g., marital status, employment) will be reported.

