All analyses will be conducted using intention-to-treat methods to minimize the risk of attrition bias. The *primary analyses* of differences in *H. pylori* eradication between the intervention and usual care groups will first be tested using a chi-squared test of binomial proportions. We will assess level of participation for those randomized into the intervention arm, and explore whether level of participation is associated with greater changes in health outcomes. Logistic regression analysis will be used to analyze differences in outcome between those who receive the intervention and those who do not, controlling for potential confounding factors. All quantitative data will be entered and analyzed using standard statistical packages (e.g., SAS, R, Stata). The primary analysis will assume that any patient lost to follow-up failed to achieve *H. pylori* eradication. As a sensitivity analysis, we will apply multiple imputation to impute missing outcomes assuming a missing-at-random mechanism.

The analysis of *secondary outcomes* is guided in part by the Social Cognitive Theory. We hypothesize that the intervention group, when compared with usual care, will report: 1) increased medication adherence; 2) increased self-efficacy for adherence; 3) improved health literacy; 4) improved knowledge about stomach cancer prevention; and 5) higher levels of perceived health related quality of life. We will compare these intermediate outcomes between groups using t-test or its non-parametric equivalent, the Wilcoxon rank-sum test. Sex as a biological variable will be addressed by exploring gender as a potential moderator of intervention effects.

Power calculations. For the control group, we conservatively estimate that approximately 55% will achieve *H. pylori* eradication based on several studies of overall and, specifically, Chinese American populations.^{36,45,46,100} We wish to detect an increase in this rate to approximately 80% in the intervention group; this difference is reasonable based on studies in Ireland and China that showed increases of approximately this magnitude in rates of knowledge and high adherence in similar populations.^{36,44,45} Accrual of 144 participants, evenly randomized to intervention or usual care, provide greater than 80% power to detect this difference, using a 2-sided, 0.05-level test.

B1a. Substudy Data Analysis.

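### Covariates for the adjusted analyses are chosen by observed baseline difference, with no threshold or list, and the tests named for the secondary scales cannot carry that adjustment; the chi-squared primary test is unaffected

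*Combined protocol and SAP*

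**What the plan says.** Section III.B1 (EHR-CHW Intervention Analysis) begins with a comparison of the arms: "We will conduct analyses to determine the comparability of the participants in the 2-arms using standard techniques, including Student's t-tests" and chi-squared tests for dichotomous variables. The rule that follows is "If the randomized groups differ in baseline characteristics, we will adjust for those variables in subsequent analyses of program effects". The baseline items named next, "Summary data on medical history, years in the US, access to and utilization of primary health care services, and social characteristics", are there for descriptive reporting and are not offered as candidate covariates.

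For eradication, the same section tests the arms first by chi-squared. It later adds a logistic regression that controls for confounders it does not name. That sentence comes straight after the analysis of level of participation and speaks of people who do or do not receive the intervention. The section's general rule is "All analyses will be conducted using intention-to-treat methods to minimize the risk of attrition bias".

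For the secondary scales, the only between-arm methods named are the t-test and the Wilcoxon rank-sum test. Section III.A2 says: "Data will be collected by study staff via surveys at baseline, 2, and 6 months". Background section B4 says that acculturation, indicated by nativity, years in the US and English proficiency, "is a significant factor that influences health access and behaviors for Chinese American immigrant communities, including impacting screening and disease prevention".

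**The concern.** In a randomised trial, baseline differences between arms arise by chance. A rule that adjusts for whatever differs selects covariates by that chance. A strong predictor that happens to be balanced is left out, and an irrelevant variable that happens to be imbalanced goes in. The acculturation indicators, which the protocol itself calls influential, would enter under this rule only if the arms happened to differ on them. The logistic model's open reference to confounders could admit balanced predictors, but it is just as unspecified.

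Three things are at stake. The adjusted effect on eradication is not fixed in advance, since it depends on what counts as a difference. The adjustment promised for later analyses of program effects cannot be made with the tests named for the scales. And the efficient use of baseline scores, which are already being collected, is not planned.

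**Working it through.** **1. The plan's own power figure.** Inputs from Section III.B1: 55% against 80%, 144 participants randomised 1:1 (72 per arm), two-sided 0.05.
- Pooled rate 0.675; SE under the null = √(0.675 × 0.325 × 2/72) = 0.0781.
- SE under the alternative = √[(0.55 × 0.45 + 0.80 × 0.20)/72] = 0.0752.
- z = (0.25 − 1.96 × 0.0781)/0.0752 = 1.29, so power = 0.901 (0.903 by exact enumeration).

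This agrees with the stated power of more than 80%. No covariate enters the calculation.

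**2. How often the rule is triggered.** The plan fixes neither the number of variables nor the cut-off. The data items and scales it mentions give about 9 candidates, or up to 15 with the scales and knowledge included. For k independent variables tested at level a, the chance that at least one differs is 1 − (1 − a)^k.

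| k (assumed) | a = 0.05 | a = 0.10 | a = 0.20 |
|---|---|---|---|
| 9 | 37% | 61% | 87% |
| 12 | 46% | 72% | 93% |
| 15 | 54% | 79% | 97% |

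**3. How far the adjusted odds ratio moves.** Simulation with 72 per arm and marginal rates held at 55% and 80%. Assumed: 12 independent baseline variables, five of them prognostic with a common odds ratio (OR) per SD. The table shows the share of trials in which the adjusted odds ratio from the same data differs by more than 10% between cut-offs.

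| OR per SD (assumed) | Across p<0.05, <0.10, <0.20 | p<0.05 against p<0.10 |
|---|---|---|
| 1.0 | about 18% | about 6% |
| 1.3 | about 27% | about 9% |
| 2.0 | about 40% | about 19% |

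Repeat runs agree to within about 2 points.

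**4. Type I error.** At 55% in both arms (16,000 simulated trials per scenario), chi-squared rejects in 5.0–5.4% and logistic regression under the rule at p<0.05 in 4.6–5.1%. If one could report whichever of four models (unadjusted, or any of the three cut-offs) was significant, the rate would be 6.2–6.8%.

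**5. Power of an adjusted eradication analysis.** With five prespecified covariates and a standardised risk difference, the change from chi-squared is −0.2, +0.2 and +1.6 points if each has OR 1.0, 1.15 or 1.3 per SD. It reaches +7.0 only if all five have OR 2.0. A Wald test in the logistic model gives about 0.4 to 0.6 points less.

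**6. Secondary scales.** Detectable standardised difference at 80% power, two-sided 0.05, 72 per arm, no loss. The t-test on follow-up scores gives 0.470 (noncentral t). Multiply by √(1 − r²) for baseline adjustment and by √[2(1 − r)] for change scores, where r is the baseline to follow-up correlation.

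| r (assumed) | Follow-up only | Change score | Baseline-adjusted |
|---|---|---|---|
| 0.3 | 0.47 | 0.56 | 0.45 |
| 0.5 | 0.47 | 0.47 | 0.41 |
| 0.7 | 0.47 | 0.36 | 0.34 |

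With 20% loss assumed (58 per arm), the follow-up figure is 0.53 and the baseline-adjusted figures are 0.50, 0.45 and 0.38.

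**The case against.** The best defence is that no decision-bearing result is touched. The primary test takes no covariates, and at one fixed cut-off the adjusted test is not anti-conservative. Both points stand, and they limit the concern.

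Scale matters too. The standard error of the log odds ratio is √[1/(72 × 0.2475) + 1/(72 × 0.16)] = 0.38, so a 10% movement (0.095 on the log scale) is about a quarter of a standard error. The plan's only stated level is 0.05; if that is meant for the baseline tests as well, much of the movement in step 3 disappears. That stands as a reason for a modest rating, but the plan does not tie that level to the baseline comparison.

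A reader might count the unadjusted result as a further reading of the rule, which raises the share of trials moving by more than 10% to 33–58%. That is not a fair count. The unadjusted comparison is already fixed, and with prognostic covariates an adjusted odds ratio differs from an unadjusted one even without selection.

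A reader might also infer that baseline scores are ignored. The text does not show that: its hypotheses speak of increases and improvements, and a t-test or Wilcoxon test can be run on change scores. What remains is that the plan does not say which is compared, and baseline adjustment does better than either at each correlation shown.

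Finally, the logistic sentence might be read as an as-received analysis. The intention-to-treat statement largely settles this, and the wording looks like loose drafting.

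**Conclusion.** The concern holds as a modest weakness of the supporting and secondary analyses, worth correcting. Section III.B1 selects covariates by chance imbalance with no threshold or list, leaves the logistic confounders unnamed, and promises an adjustment that the tests named for the scales cannot deliver.

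It does not support a claim that the primary result is compromised, that type I error is inflated by the rule at a single cut-off, or that adjustment would bring a material gain in power for eradication. That gain starts at about zero and depends on prognostic strength that the documents do not give. The surer benefit is in the scales: a detectable difference of 0.45, 0.41 or 0.34 with baseline adjustment, against 0.47 for follow-up scores.

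The figures rest on assumed candidate counts, independence between variables, cut-offs, prognostic strengths and correlations. Variables such as years in the US, language and health literacy may well be correlated, which would change the percentages. The lack of prespecification does not depend on any of these assumptions.

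**What to change.** - Describe baseline characteristics without tests, and drop selection by baseline comparison.
- Before outcome data are seen, name a short covariate set from data already collected, with a reason for each (for example facility, age, sex, years in the US and baseline health literacy). Let it replace the unnamed confounders.
- Fit that set by randomised arm, whatever the observed balance, as a supporting analysis. State that the unadjusted chi-squared test is decisive, and label any as-received model exploratory.
- Keep adjustment for observed imbalance as a labelled sensitivity analysis, so that the freedom to respond to a chance imbalance is not lost.
- Analyse each scale that the baseline survey contains by linear regression on arm and its baseline value.

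The change is to SAP wording; it needs no new data and no change in sample size. There are two costs. If the covariates are not prognostic, power of the adjusted eradication model falls by about 0 to 1 point. If a standardised risk difference is reported, its null rejection rate was slightly raised in simulation (5.5–5.7%, against 5.0–5.4% for chi-squared), so either use a small-sample variance correction or keep chi-squared as the sole test.

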During the intervention period, patients that meet the eligibility criteria will be identified. The bilingual CHWs will complete a brief screening form with potential participants in person or via phone (See *Script for Telephone Screening and Screening form*). The screening form will assess demographic characteristics, participant eligibility, interest in our program, and reasons for refusal to participate. For in-person screenings, if the patient is eligible and interested in the study, the CHW will obtain verbal informed consent for study participation and describe the randomization process (See *Combined Verbal Informed Consent*). For individuals identified from the EHR registry list, CHWs will conduct phone screenings, and will complete the verbal consent process by phone with interested, eligible individuals. CHWs will compile and share contact information for consented study participants with the study coordinator on a weekly basis. All consented participants will be randomized in a 1:1 ratio using a computer-generated randomization⁸⁷ scheme to one of the study arms.

Consented participants randomized to the EHR-CHW intervention arm will receive a standardized protocol. The protocol, designed to be flexible, consists of 4 educational sessions to be delivered in a group, or per the participant's preference one-on-one or via telephone or other social networking platforms (eg. WeChat). The sessions employ adult learning techniques and group-based learning activities. All session materials will be culturally and linguistically adapted. The in-person sessions will be held at the clinics and community spaces identified by partner agencies. Data will be collected by study staff via surveys at baseline, 2, and 6 months. Scheduled office visits will be tracked via data pulls from the EHR system. If no visit is scheduled during the follow-up period, project CHWs will conduct follow-up calls to schedule participants for data collection events in the community, at the clinic, or in their home, with permission.

C 3. Assessment of Implementation, Adoption, Sustainability, and Scalability

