To capture data on utilization patterns of the tailored EHR decision support, provider feedback tools and integrated EHR-CHW initiatives, [name] will work with MCIT to extract system files monthly that indicate date and time stamps and user logins for each time the tools were used and/or CHW embedded templates were accessed. Data will be extracted into a spreadsheet and analyzed by the study staff.

Qualitative key informant interviews (See *Key Informant Interview Guide*) will be conducted by study coordinator with key providers (1-3 at each site), administrators (1-2 at each site), and the CHWs (1 at each site). At baseline, the interviews will be incorporated into the workflow analysis to assess current satisfaction and EHR usage and health coaching. At follow-up, the interviews will assess barriers and facilitators to the implementation and adoption process of the integrated EHR-CHW intervention, intervention fidelity, and to solicit recommendations for the replication and scalability of the intervention to other clinical sites. Questions will be adapted from existing validated measures on acceptability, feasibility, adoption, organizational culture, and scalability.⁸⁸⁻⁹³

Qualitative ethnographic data will be collected through observations at the clinic sites. Ethnographic data will be collected by CHWs in Year 1 and by the study coordinator in Year 5 and will be guided by the 5 key steps in a rapid assessment process. Observations will occur in clinic waiting and administrative areas. Fidelity checklists will be conducted during CHW educational sessions and follow-up.

C4. SUBSTUDY

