Inclusion Criteria: An individual is eligible for the intervention if s/he: a) self identifies as Chinese American; b) is an outpatient aged 21+; c) plans to continue to live in the region during the next 12 months; d) is willing to be randomized to either treatment or control groups; and e) has a confirmed diagnosis of *H. pylori* infection by at least one of the following methods: C-urea breath test, histology, rapid urease test or bacterial culture, fecal stool antigen test or other clinically approved *H. pylori* infection diagnostic test.⁹⁴

Exclusion Criteria: The exclusion criteria include: a) advanced chronic disease that would not allow the patient to complete follow-up or attend visits; b) allergy to any of the treatment drugs; c) previous gastric surgery; d) pregnancy or currently breastfeeding; e) taking antibiotics or bismuth salts within 2 weeks before the study.

Rationale for proposed exclusion of gender and racial/ethnic group members: Individuals from other racial/ethnic groups are excluded from participation in the intervention as this study is focused on Chinese American adults. Men and women will both be invited to participate in this intervention. No children or vulnerable subjects will be enrolled in this study.

Substudy

Inclusion criteria: An individual is eligible for the substudy if s/he is: a) enrolled in the EHR-CHW Intervention main study; and b) is willing to provide either an oral sample, a fecal sample, or both. Individuals will be excluded from the substudy if they are unable to mail the samples back to the study team.

Key Informant Interviews

Inclusion Criteria: Interviewees must be an adult (18 years and over) and they must be a provider, an administrator, or a community health worker. Individuals will be excluded from the interview if the interview cannot be conducted in the English language.

III. METHODS & PROCEDURES

A. Methods & Procedures

A1. EHR-CHW Intervention Components

EHR Component

Epic, the EHR system, has been integrated at NYU Langone Health, and is being implemented at Bellevue and Gouverneur Hospitals. [name] will oversee MCIT in creating the proposed EHR enhancements.

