The integrated EHR-CHW protocol will support team-based care by supporting feedback between clinic staff and CHWs, including: First, templates will be created that CHWs can complete and upload into the EHR. Healthcare providers will be able to access these templates using EHR and building upon existing workflow. Second, health coaching and referral materials, to be developed by the advisory committee, will be made available to providers through the EHR. Third, CHW communication with the healthcare

team will be facilitated by participation and report-backs from CHWs during regular team “huddles” or staff meetings; the frequency of participation will be site-specific and determined by findings from the workflow analysis.

Integrated EHR-CHW Protocol Intervention.

Orientation, Implementation and Training. CHWs have been trained through the NYU-CUNY Prevention Research Center Training Program in a set of core competencies, which was developed by CSAAH faculty [name] and [name].⁹⁵

Enrollment & Randomization. *H. pylori* infected individuals will be identified and recruited into the study from NYC health care facilities (NYU Langone Health – which includes NYU Langone Brooklyn, NYU Langone Brooklyn Family Health Centers and affiliated provider practices, and NYU Ambulatory Care Centers – Bellevue Hospital Center and Gouverneur Hospital). Participants will be identified by 2 approaches: 1) using ICD codes for *H. pylori* and Chinese ethnicity identified through a race and language code available in EHR, with recently diagnosed *H. pylori* infection (within 7-days) will be identified; via a EHR registry list, and 2) patients will be recruited directly from the above mentioned clinics. All consented participants will be randomized in a 1:1 ratio using a computer-generated randomization scheme⁸⁷ to one of the study arms.

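### The primary chi-squared test and the power statement allow neither for possible correlation within community health worker or session group in the intervention arm nor for site

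*Combined protocol and SAP*

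**What the plan says.** **Allocation.** Section III.A1 (Enrollment & Randomization) states: "All consented participants will be randomized in a 1:1 ratio using a computer-generated randomization" scheme. Section C2 says the same. Neither mentions strata or blocks.

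**Delivery.** The intervention protocol in section C2 "consists of 4 educational sessions to be delivered in a group", or one-on-one, by telephone or on a social platform if the participant prefers. Control patients have no such sessions. Group size, the number of CHWs who deliver sessions and the patients per CHW are not given. The only count is in the list of people to be interviewed (section C3), which ends "and the CHWs (1 at each site".

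**Sites.** Several facilities take part. Section III.A1 (EHR Component) says the record system is integrated at one health system "and is being implemented at Bellevue and Gouverneur Hospitals".

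**Analysis (section III.B1).** Eradication "will first be tested using a chi-squared test of binomial proportions". Logistic regression with unnamed confounders follows, and variables that differ at baseline are to be adjusted for. Site, CHW and group are not named.

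**Power (section III.B1).** For controls, "we conservatively estimate that approximately 55% will achieve *H. pylori* eradication", against about 80% with the intervention. "Accrual of 144 participants, evenly randomized to intervention or usual care, provide greater than 80% power to detect this difference", "using a 2-sided, 0.05-level test". No design effect or ICC is mentioned.

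**The concern.** This is a partially nested design: patients are randomised singly, but in one arm they are then treated by a shared person and sometimes in a shared group. The CHWs coach adherence and send follow-up reminders, and a patient lost to follow-up counts as a failure. A CHW's skill or diligence could therefore move the primary outcome, in the intervention arm only. If it does, the intervention-arm proportion varies more than the binomial variance in the chi-squared test allows, the p-value is too small, and the power figure is too favourable.

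Site raises a different issue. Sites at different stages of EHR rollout may differ in eradication or in follow-up testing. A test that ignores site leaves chance imbalance between arms in the estimate and gives up precision.

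**Working it through.** **1. The plan's own figure.** Inputs from section III.B1: 72 per arm, 55% against 80%, two-sided 0.05. The pooled proportion is 0.675. The null SE is sqrt(2 × 0.675 × 0.325 / 72) = 0.0781, and the alternative SE is sqrt((0.55 × 0.45 + 0.80 × 0.20)/72) = sqrt(0.4075/72) = 0.0752. Power = Φ((0.25 − 1.96 × 0.0781)/0.0752) = 90.1%, or 86.5% with continuity correction. The stated power above 80% is reproduced under independence.

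**2. Clustering in the intervention arm only.** With m patients per cluster, DE = 1 + (m − 1) × ICC multiplies the variance of that arm alone.
- Ratio of true to assumed null SE: r = sqrt((1 + DE)/2).
- Approximate type I error of the planned test: 2 × (1 − Φ(1.96/r)).
- Power with the SE corrected: Φ(0.25/SE − 1.96), where SE = sqrt((0.2475 + 0.16 × DE)/72).

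The values of m and ICC are assumptions. Groups of 6 illustrate session clustering, and 24 per CHW is 72 patients over three CHWs. Simulated type I error draws the intervention arm from a beta-binomial with mean 0.675.

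| m | ICC | DE | r | Type I, formula | Type I, simulated | Corrected power |
|---|---|---|---|---|---|---|
| 6 | 0.02 | 1.10 | 1.025 | 5.6% | 5.4% | 90% |
| 6 | 0.05 | 1.25 | 1.061 | 6.5% | 6.2% | 89% |
| 6 | 0.10 | 1.50 | 1.118 | 8.0% | 8.0% | 86% |
| 24 | 0.02 | 1.46 | 1.109 | 7.7% | 7.8% | 86% |
| 24 | 0.05 | 2.15 | 1.255 | 11.8% | 12.0% | 79% |
| 24 | 0.10 | 3.30 | 1.466 | 18.1% | 18.8% | 67% |

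Example, m = 24 and ICC 0.05: SE = sqrt((0.2475 + 0.344)/72) = 0.0906, and 0.25/0.0906 − 1.96 = 0.80, so power is 79%.

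The last column uses the alternative variance throughout. Using the inflated pooled variance for the critical value, as in step 1, gives 89%, 87% and 83% for groups of 6, and 84%, 74% and 60% for 24 per CHW. On that stricter basis power stays at 80% while DE is at most about 1.72, that is, ICC up to 0.72/23 = 0.03 for 24 per CHW or 0.72/5 = 0.14 for groups of 6. Both versions use normal critical values. With only a handful of CHWs, a small-sample correction would lower power further.

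**3. Site effects shared by both arms.** With four assumed sites, unstratified individual randomisation and a site ICC of 0.05 to 0.20, the simulated type I error of the unadjusted test was 5.3% to 5.5%, against 5.4% with no site effect. Validity is not affected.

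**4. Precision lost by ignoring site.** Assume three equal sites and a common odds ratio of (0.80/0.20)/(0.55/0.45) = 3.27, with allocation unstratified. Simulated power, chi-squared against site-stratified Cochran-Mantel-Haenszel:
- Control rates 40/55/70%: 87.4% against 88.7%, a gain of 1.3 points.
- Control rates 30/55/80%: 79.8% against 85.7%, a gain of 5.9 points.
- No site difference: a loss of about 0.4 points.

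**The case against.** The strongest reply is that the large figures rest on facts the documents do not contain.

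- **One CHW per site.** A reader might infer this from the interview list, but that list counts interviewees. Section II expects about 10 to 12 informants. At 3 to 6 per site this suggests roughly two to four sites, so one CHW each would mean 18 to 36 intervention patients per CHW. That is an inference, and the rows for 24 per CHW are conditional on it.
- **Session groups may be small.** Table 4 gives 15 recruiting quarters, so 72/15 = 4.8 intervention patients per quarter across all sites. Participants may also choose one-on-one or remote sessions. Groups of 2 would give a type I error of only 5.0% to 5.5% at ICC 0.02 to 0.10. This stands for groups, but individual and telephone sessions still share a CHW.
- **Site.** A reader might infer that several sites without stratification make the chi-squared standard error wrong. They do not (step 3): an unadjusted test matches unstratified individual randomisation. Nor do the documents say that the list is unstratified; they are silent.
- **CHWs as fixed.** If inference is confined to the CHWs employed, the CHW inflation is not called for. This is a fair position, but the study aims at a reproducible model that can be scaled to other sites, which reaches beyond those CHWs.
- **Existing adjustment.** The logistic regression could include site. It does not name it, and adjustment prompted by observed baseline differences is not a pre-specified site-stratified test.
- **Few clusters.** A random effect or robust variance with about three CHWs has almost no degrees of freedom. This stands, and is why the nested analysis should be a sensitivity analysis and not the primary one.

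**Conclusion.** The point holds as an omission with a conditional cost. Neither the primary test nor the power statement allows for CHW, group or site. If the ICC in the intervention arm is zero, the test is sound and power is about 90%. If it is above zero, the test is anti-conservative: slightly for small groups, and materially if a few CHWs each carry many patients, where an ICC of 0.05 would more than double the nominal 5% error. The ICC, group size and load per CHW are all assumptions.

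Two stronger conclusions are not supported. The standard error cannot be called wrong outright, because the documents establish no correlation. The stated power cannot be called false: it holds under independence and for groups of 6 up to ICC 0.10. It falls below 80% only in the heavier CHW scenarios. Ignoring site is a matter of precision, and the gain of 1 to 6 points depends on assumed differences between sites.

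**What to change.** 1. **Site.** Make the primary test Cochran-Mantel-Haenszel, or logistic regression, stratified by site. If the present scheme has no strata, stratify the list by site for remaining patients, with concealed and varying block sizes so that CHWs who recruit cannot predict allocation. The consent section shows that patients were enrolled under earlier protocol versions, so fix the change before anyone sees outcomes by arm.
2. **Clustering.** State the number of delivering CHWs and the expected group sizes. Record CHW, session-group ID and mode of delivery. Pre-specify as a sensitivity analysis a partially nested model: clustering in the intervention arm only, each control its own cluster, small-sample correction, ICC reported. The site-stratified test does not deal with CHW clustering, so the plan should say that it governs the primary conclusion and the nested analysis qualifies it.
3. **Power.** State that the figure assumes independence, and show it over a range of ICCs and cluster sizes.

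The cost is a revised list for remaining patients, three data fields and wording in the analysis section. The stated power becomes less favourable, and intervals in the sensitivity analysis somewhat wider. If there is one CHW per site, CHW and site effects cannot be separated and the ICC will be imprecise.
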